Impact of combining rTMS with motor training (Aim 2b): Motor training strategies used in individuals with cervical SCI often focus on increasing volitional arm muscle activation through strength training, electrical stimulation, and general exercises (see Spooren et al., 2009). While these studies reported that motor training enhances hand motor function, behavioral improvements remain limited. Over the last decades, high frequency rTMS applied over the motor cortex has been shown to induce changes in motor cortical excitability (see section above). Since the mechanisms underlying these effects are related to CNS plasticity, rTMS has been combined with motor training as a tool for enhancing motor function in individuals with movement disorders.

Impairment in motor function is a major deficit in veterans with spinal cord injury (SCI). While rehabilitative interventions have shown success in improving aspects of hand motor function their overall effects remain limited. The goals of this study are to examine the physiology of nervous system pathways contributing to the control of movements after cervical SCI, and to promote the recovery of upper and lower extremity movements by using non-invasive brain stimulation and motor training. We focus on both hand and arm function, which are necessary for most of our daily-life activities, as well as lower extremity movement; therefore, our results may directly impact the quality of life for veterans and their caregivers by enhancing their independence and level of care.

C. Study Design

This study will focus on two basic aspects involved in upper and lower extremity motor function, and how these are affected after chronic SCI using a randomized sham control design with single blind.

Methodology:

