This study will consist of electromyography (surface and intramuscular), peripheral nerve stimulation, and transcranial magnetic stimulation, electrical stimulation, of the hand, arm, leg, and foot representation of the primary motor cortex, as well as MRI scans of the brain. We will examine the physiological measurements of upper and lower extremity muscles (such as in the first dorsal interosseous (FDI), biceps brachii (BIC), anterior deltoid (AD), tibialis anterior (TA), hamstring (HAMS) and quadriceps (QUAD)). This study may occur at the Miami Project to cure Paralysis at the University of Miami. We will include subjects between the ages of 18 and 85, both healthy controls and individuals with chronic spinal cord injuries that occurred at least 6 months prior to recruitment. Both healthy controls and those with spinal cord injuries will be able to perform small hand and arm movements and small leg and foot movements. The primary outcome measures of this study are muscle responses to stimulation with magnetic pulses using TMS and electrical stimulation of a peripheral nerve in the arm or leg. We propose to enhance the recovery of motor function by using new protocols of high frequency non-invasive repetitive TMS (rTMS) and motor training. Repetitive TMS will be used during hand, arm, leg and foot movements in a task-dependent manner to induce cortical plasticity and enhance voluntary output of the muscles associated with those movements. Second, rTMS will be applied in a task-dependent manner during a visuo-motor training task that also involves movements of the hands, arms, legs or feet.

Phase 1

Aim 1. Neural Control of Movements in SCI and Control Subjects

We will use TMS, CMEPS, and peripheral nerve stimulation to test the hypotheses that 'precision grip and wrist movements will be associated with reduced motor cortical (as measured by intracortical inhibition) and spinal inputs (as measured by F-wave persistence and amplitude) to hand and wrist motoneurons after cervical SCI compared to controls'. Subjects will be instructed to perform a precision grip (between index and thumb) and simultaneously wrist flexion or extension movements. Measurements of cortical and motoneuronal excitability will be acquired during movement.

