Each testing session will be separated by at least two days. Subjects will be instructed to perform a precision grip (between index and thumb) and simultaneously wrist flexion or extension movements. Measurements of cortical and motoneuronal excitability will be acquired during movement. Tasks involving lower-limb movement will also be tested as control tasks. In each session, we will use the following experimental setup and motor tasks:

Experimental setup – During testing, individuals will be seated in an armchair with both elbows flexed at 90°. Each arm will be supported by a custom device attached to a potentiometer to measure wrist flexion and extension angles and a load cell to measure grip forces. Index fingers and thumbs will be positioned in a customized gripping tube attached to a two-axis load cell. Subjects who cannot be transferred will be tested in their wheelchair by using customized platforms that we previously used in individuals with SCI. Surface electrodes will be positioned bilaterally on the skin overlying upper and lower-limb muscles in a bipolar montage (inter-electrode distance approximately 2 cm). The amplified EMG signals will be filtered, sampled, and stored for analysis. Forces will be measured by load cells and angles by potentiometers and stored for analysis.

Motor task – In a first test, subjects will be instructed to perform full wrist flexion and simultaneously perform a precision grip (between index and thumb) with one hand. In a second test, subjects will be instructed to perform full wrist extension and a precision grip with one hand. At the start of testing,

individuals will perform 3 brief precision grip maximum voluntary contractions (MVCs) (3–5 s) and wrist flexion and extension MVC with 30 seconds of rest. Custom software will be used to acquire signals from potentiometers and load cells to display visual feedback corresponding to wrist flexion and extension angles and 10% of MVC grip force. Subjects will be instructed to move a cursor at a comfortable speed and to hold the cursor in the target force and position for 2-4 seconds. During lower-limb tasks subjects will be instructed to move as cursor by performing ankle dorsiflexion and plantar flexion movements. Approximately thirty repetitions of each task will be randomly tested.

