(B). Motoneuronal excitability (reflected by F-wave persistence and amplitude): F-waves will be tested by using supra-maximum stimulus intensity (120% of the maximal motor response) to the ulnar nerve at the wrist and the median nerve at the elbow. The anode and cathode will be approximately 3 cm apart and 1 cm in diameter. We will examine F-waves in first dorsal interosseous, flexor and extensor carpis radialis muscles.

Phase 2

Aim 2a. Enhance recovery of motor function by using non-invasive repetitive transcranial magnetic stimulation (rTMS)

To accomplish this aim we propose to complete two main experiments. First we will use rTMS to test the hypothesis that *rTMS induced cortical plasticity during movement will enhance voluntary output in hand muscles (as measures by electromyography and Jebsen Taylor Test) after spinal cord injury (Aim 2a)*. Second, we will combine precision grip and wrist training with rTMS to test the hypothesis that *precision grip training outcomes will be enhanced by rTMS induced cortical plasticity (aim 2b)*.

Experiment 1 (Aim 2a)

Participants will be randomly assigned to three groups: (1) rTMS, (2) Sham rTMS and (3) sham rTMS over control brain area. Randomization will be performed by lottery (i.e. Drawing from an envelope a piece of paper indicating the intervention). In the first two groups, rTMS stimulation will be targeting finger and wrist muscles during precision grip and write voluntary contractions. In the last group, rTMS will be applied over the dorsolateral prefrontal cortex (DLPFC) or at the leg presentation of the primary motor cortex, or at other related control area as needed. Each subject will be asked to participate in all sessions separated by a washout period of approximately one week. During testing, subjects will be seated in an armchair with both arms flexed at the elbow by 90 degrees. In each group we will use the same apparatus described in Aim1. At the start of the experiment subjects will perform 3 brief MVCs (3-5s) into index finger abduction and wrists flexion and extension, separated by 30 seconds. The maximal forces will be used to set targets for subsequent submaximal contractions.

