sentence, (ii) turning over 3×5 cards, (iii) picking up small common objects such as a paper clip, bottle cap and coin, (iv) simulated feeding using a teaspoon and 5 kidney beans, (v) stacking checkers, (vi) picking up large light objects (empty tin cans), and (vii) picking up large heavy objects (0.5 kg tin cans). The time to complete each task was recorded in seconds. The affected hand was tested first. Subjects were allowed a maximum of 180 s to complete each sub-test. If the subject could not complete the task within the time allowed, 180 s was taken as the completion time to avoid fatigue (109).

ASIA examination

- ASIA 2002; Marino et al., 2003
- Pin prick with a safety pin and light touch with a cotton ball are tested. For pinprick the result is graded as 2- normal; 1- impaired where difference between sharp and dull is appreciated but less; 0- difference could not be appreciated between sharp and dull. For light touch 2- reports when touched and feels the same as face 1- reports touched but less than in face 0-does not reliably report being touched
- The dermatomes tested are C2 - occipital protuberance behind the ear C3 - supraclavicular fossa C4 - AC joint apex (C4 may extend down the chest almost to the nipple line) C5 - lateral antecubital fossa C6 - dorsal surface of proximal phalanx of thumb C7 - dorsal surface of proximal phalanx of middle finger C8 - dorsal surface of proximal phalanx of little finger T1- medial antecubital fossa T2- axilla apex T4- nipple line T6 - xiphisternum T10 - umbilicus T12 - inguinal ligament midline L1,23 - thigh L4- medial malleolus L5 - dorsum of foot at 3rd MTP joint S1- lateral heel S2- popliteal fossa S3- ischial tuberosity S4,5 - perianal region
- Optional sensations that can be tested are joint movement (reported as absent, impaired - correct in 8/10 of large joint movements only or normal-correct 8/10 of large and small movements both) , deep pressure sensation (reported as present or absent)

Electrical Perceptual Threshold

The EPT method uses incrementing electrical stimulation and the method of limits to determine sensory threshold. (Ellaway and Catley 2013; Macklin and Perez et al, 2015).

Chedoke Arm and Hand Activity Inventory

The purpose of this is to evaluate the functional ability of the hemiplegic arm and hand to perform tasks. The performance of the affected limb is scored using a 7 point activity scale ranging from total assistance to complete independence.

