The TMS system stimulates the brain non-invasively. It generates a small magnetic field across the subject. TMS is widely used in clinical research, and the risks of TMS are believed to be very low. However, there is the very slight chance that TMS can cause a seizure. There is no ionizing radiation exposure involved and the studies are non-invasive. All participants will be screened before enrollment to assure that they meet study criteria and that there are no contraindications to TMS.

Subjects will be instructed that they can discontinue the TMS experiment at any time. In the unlikely event of a seizure, a medical physician will be contacted for immediate response. If a headache or mild scalp discomfort occurs, subjects will be directed to use over the counter pain medication at their own discretion. Earplugs will be utilized to minimize any type of hearing damage that might possibly occur due to the sound generated by the TMS equipment. [name] (PI) and/or an authorized team member will conduct TMS procedures as needed.

[name] has been working with TMS procedures for the last 13 years and has extensive experience in the use of TMS procedures. Although very unlikely, it is theoretically possible that the participant may have a seizure induced by the TMS. Considering the large number of subjects and patients who have undergone TMS studies since 1998 and the small number of seizures, we can assert that the risk of TMS to induce seizures is certainly very low (see review by Rossi et al., 2009). However, we will inform the participant about this unlikely risk. If a seizure occurs, it will occur during the TMS application itself, not after. When a seizure happens the participant's brain starts acting strangely and participants may feel dizzy and have repetitive rhythmic movements of any part of their body. If this unlikely event happens, we will immediately call an attending physician. On weekends, the subject should call the emergency 24 hour [contact] to get in touch with [name], and let him know that he is a research subject from the Miami VA in Enhancement of Motor Function after Spinal Cord Injury.

In the unlikely event of a seizure, a standard seizure protocol will be followed:

1. Cushion the head and area so subject does not injure themselves.
2. Turn the subject on their side to prevent aspiration
3. Monitor the duration of the seizure

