Screening Interview: Identifiable information collected during either the screening interview will be destroyed if the potential subject does not qualify. If the subject does qualify and ultimately enrolls into this research, all information collected will become part of their research record. All security precautions that are reflected in this protocol will apply.

Data Collection and Storage: Research records will be retained in accordance with the Veterans Health Administration (VHA) Records Control Schedule. The Federal Privacy Act protects the confidentiality of medical records. Electronically-stored medical information collected from study participants will be kept on a VA server. Electronic data recorded during experimental sessions will be kept on fully-secured computers (password protected) on a VA server. Unique subject identifiers (i.e., a code accessible only to the PI and AI) will be used to label all electronic data files.

F. Sample Size

Up to 500 participants (250 SCI, and 250 control subjects) will be recruited to participate in this study at the VAMHS and at the University of Miami. Based on our previous protocols testing spinal cord injured subjects and healthy control subjects, we have added a 25% attrition rate to the number of subjects we plan to enroll in the study.

All participants will be between 18 and 85 years of age. We plan to recruit both veterans and non-veterans.

G. Data analysis is consistent with the study objective

Aim 1: Repeated-measures ANOVA and Tukey post hoc test will be used to assess the effect of TASK (rest, precision grip/wrist flexion, and precision grip/wrist extension) and GROUP (SCI, controls) on physiological measurements.

Aim 2a: Repeated measures ANOVA and Tukey post hoc test will be used to determine the effect of TIME (0,10, 30, 60 min after a single rTMS session), STIMULATION (rTMS, sham rTMS over control brain area) on physiological and behavioral measurements.

Aim 2b: repeated measures of ANOVA and Tukey post hoc analysis will be used to determine effects of GROUP (training + rTMS, training + sham rTMS), TIME (sessions number 1,5,10 and follow up 1,2, and 3 months) on physiological outcomes and motor performance.

H. Privacy and Confidentiality:

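### The single-blind design provides neither masked scoring of recordings nor an assessor unaware of allocation, so assessment bias is open for F-wave persistence and for the timed and graded tests

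*Combined protocol and SAP*

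**What the plan says.** All references are to the combined protocol and SAP.

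- **Blinding.** Section C gives the design as "using a randomized sham control design with single blind". It does not say which role is blinded.
- **Allocation.** Under Experiment 1 (Aim 2a), assignment is by lottery: "Drawing from an envelope a piece of paper indicating the intervention". Experiment 2 (Aim 2b) uses the same method. The person who draws is not named.
- **Sham.** Under the training plus sham group of Experiment 2, one coil rests on the head and a second, behind the head, is the only one fired. The text describes what the participant may feel and hear.
- **Who stimulates.** Section E, TMS procedures: "PI) and/or an authorized team member will conduct TMS procedures as needed".
- **Primary outcome.** Methodology in section C: "The primary outcome measures of this study are muscle responses to stimulation with magnetic pulses using TMS and electrical stimulation of a peripheral nerve".
- **How it is recorded.** Aim 1, experimental setup: "The amplified EMG signals will be filtered, sampled, and stored for analysis". Part (B) of Aim 1 adds "Motoneuronal excitability (reflected by F-wave persistence and amplitude", with no criterion for when an F-wave counts as present.
- **Timed and graded tests.** The Jebsen Taylor test is timed in seconds, with a limit of 180 s per sub-test. For the Chedoke inventory, "The performance of the affected limb is scored using a 7 point activity scale ranging from total assistance to complete independence". ASIA sensation is graded 0 to 2. The Modified Ashworth Scale is used for spasticity. No timer or rater is named for any of them.
- **File coding.** Section E, Data Collection and Storage: "Unique subject identifiers (i.e., a code accessible only to the PI and AI) will be used to label all electronic data files".

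**The concern.** A sham coil deals with what participants expect. It does nothing about what the person who times, rates or reads a trace expects. If that person knows the arm, small leanings in starting a stopwatch, choosing between adjacent grades or accepting a faint F-wave can all run in the same direction. Randomisation does not remove such a shift, the planned repeated-measures ANOVA cannot tell it from a treatment effect, and a larger sample makes it more likely to be declared significant.

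This reaches outcomes that matter here. F-waves are responses to peripheral nerve stimulation and so fall within the primary outcome. The Jebsen test is named in the Aim 2a hypothesis. Jebsen, Chedoke and ASIA sensory scores are Aim 2b outcomes and are repeated at 1, 2 and 3 months.

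**Working it through.** **Step 1. Who is masked, from the text.** The steps that keep something from anyone are aimed at the participant: the sham is described by the participant's sensations, and after rTMS in Aim 2a participants are not told whether the feedback shown is current or earlier performance. Whoever fires the coils must know which coil to fire. In the control-area condition of Aim 2a, whoever places the coil can see where it is. No step masks staff.

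**Step 2. Does the file code mask the scorer?** It labels files by subject and sits under data storage. The PI is one of the key holders and is also named as a person who may deliver TMS. Nothing says that arm or time point is hidden from the scorer. The code protects privacy and does not mask scoring.

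**Step 3. Which outcomes are exposed?**

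| Outcome | Rule in the text | Exposure |
|---|---|---|
| F-wave persistence | none for presence of a response | open |
| MEP, SICI | 30 MEPs averaged; 25 test and conditioning stimuli for SICI; scorer not named | open only where judgement enters |
| IHI | no averaging or scoring rule; scorer not named | open only where judgement enters |
| Force onset | 2 SD above baseline | less exposed |
| Force rate, area, duration | defined from onset, target or decay | less exposed |
| Jebsen, Chedoke, ASIA, Ashworth | timed or graded live; assessor not named | open |

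Ashworth is described in the protocol but is not in the Aim 2b motor-function list, so it carries less weight.

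**Step 4. Illustration of size.** The plan has no figure on this point to reproduce. Section F gives only a ceiling of 250 + 250 = 500 participants with 25% attrition included. It gives no numbers per arm, and sections F and G state no alpha, power or SD. Everything below is assumed: a shift of δ SD in one arm, n per arm, no true effect, and a two-sided 5% normal test.

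Standard error in SD units = √(2/n), so the standardised shift is δ√(n/2), and

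error = 1 − Φ(1.96 − δ√(n/2)) + Φ(−1.96 − δ√(n/2)).

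The upper n is 250/2 = 125, the SCI ceiling split into two arms. The others are round values.

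| n per arm | √(n/2) | δ = 0.1 | δ = 0.2 | δ = 0.3 |
|---|---|---|---|---|
| 20 | 3.162 | 6.2% | 9.7% | 15.8% |
| 50 | 5.000 | 7.9% | 17.0% | 32.3% |
| 125 | 7.906 | 12.4% | 35.3% | 66.0% |

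Worked corners:
- n = 20, δ = 0.1: shift 0.316, error = 1 − Φ(1.644) + Φ(−2.276) ≈ 0.062.
- n = 125, δ = 0.3: shift 2.372, error = 1 − Φ(−0.412) + Φ(−4.332) ≈ 0.660.

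**The case against.** The strongest reply is that the primary outcome is captured by instrument and largely averaged, that force measures follow stated rules, and that the documents never say that the person who stimulates also assesses. All of that is correct. It narrows the point without removing it: F-wave persistence has no rule, the live tests have no named assessor, and nothing keeps the two roles apart.

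Four stronger readings are tempting and should not be drawn.

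- A reader might infer that the coil operator draws the slip and then times and rates the same participant. The text names none of these people. Only the coil operator's knowledge of the arm follows from the sham set-up, and even participant blinding is an inference, though a strong one.
- A reader might infer that force onset, or all evoked responses, are marked by hand. Force onset has a 2 SD rule, and nothing says how MEPs are measured.
- A reader might infer a definite false-positive rate for this trial. The documents give neither a shift nor arm sizes, and a two-arm normal test is not the planned repeated-measures ANOVA. It fits Aim 2a least, since each subject is asked to take part in all sessions with a washout.
- A reader might infer that masked scoring is free. The documents give no staffing or cost information, and recoding and scheduling both take effort.

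**Conclusion.** The point holds as a gap in the plan: the blinded role is not named, and there is neither masked scoring nor an assessor unaware of allocation. Bias is open, not shown to have occurred. It is clearest for F-wave persistence and the live functional and sensory tests, conditional for the other evoked responses, and smaller for the force measures.

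The range of about 6% to 66% shows only how a nominal 5% error behaves under assumed shifts of 0.1 to 0.3 SD and assumed arms of 20 to 125. It is not an estimate for this trial, and it concerns a simple two-arm comparison.

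The change is worth making because the recordings are already stored and labelled by subject, so the part that protects the primary outcome needs little more than recoding.

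**What to change.** 1. State in section C which roles are blinded.
2. Score all stored EMG, force and motion-capture recordings, including MEP, SICI, IHI and F-waves, from files recoded by a team member who does not score them, with arm and visit order hidden. Write down a fixed criterion for detecting an F-wave before scoring starts. Stored recordings already collected can be rescored in the same way.
3. Where the existing team allows, have the Jebsen, Chedoke, ASIA and Ashworth tests given and scored by a member who neither allocated nor stimulated that participant and who is kept unaware of the arm. Separating the roles is not enough if the assessor still knows the arm.

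**Cost.** Protocol wording, file recoding and some scheduling effort. Treatment, visits and sample size do not change. Item 2 can be done within the team provided that one member recodes and another scores; item 3 depends on staffing that the documents do not describe.

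**What remains.** Recoding does not protect the live tests, which rest on item 3. Neither item covers choices made while recording, such as motor thresholds and stimulus intensity, so the report should acknowledge that limit.

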During these motor tasks we will examine: (A) TMS measurements and (B) motoneuronal excitability in the first dorsal interosseous, and flexor and extensor carpis radialis muscles. TMS and peripheral nerve stimulation pulses will be delivered when subjects reach a certain degree of wrist flexion or extension and a certain percentage of MVC in the precision grip. Stimulation will be triggered if both goals are reached. This window in both directions will be modified for individuals who showed more difficulties in performing the movement in either direction.

(A) TMS measurements- Transcranial magnetic stimuli will be delivered from a stimulator through a figure-eight coil. TMS will be delivered to the optimal scalp position for activation of the left or right first dorsal interosseous, and flexor and extensor carpis radialis muscles. The TMS coil will be held to the head of the subject with a custom coil holder while the head is firmly secured to a headrest by straps to limit head movements. TMS measurements during precision grip and wrist movements will include the following:

MEPs – Resting and active motor thresholds (RMT and AMT) will be tested in each of the muscles. For this testing, TMS intensity will be adjusted to produce an MEP of 50% of the maximal MEP on each muscle tested. 30 MEPs will be average in each condition. Cervicomedullary Motor Evoked Potentials (CMEPs): Supramaximal electrical stimulation will be administered posterior to the mastoid process to elicit motor evoked potentials to upper and lower limb muscles.

Short-interval intracortical inhibition (SICI) – A conditioning stimulus (CS) will be set at an intensity of 70% of AMT. The test stimulus (TS) will be adjusted to produce an MEP of 50% of MEP-max. Test stimuli will be delivered 2.5 ms after CS. 25 TS and CS will be averaged in each condition.

Interhemispheric inhibition (IHI) – A supra-threshold CS will be set at an intensity above the RMT and given 10-50 ms before a TS delivered to the contralateral motor cortex. The coils will be positioned at the optimal location for activating the muscle tested and attached to coil holders.

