rTMS protocol- rTMS will be applied by a magnetic stimulator through a figure of eight coil with the same coil position as in Aim1. rTMS will consist of a total of 1200 pulses at an intensity of 80% of the AMT applied during a precision grip. At each time three targets will be presented on a computer screen. Each target will indicate a GO signal to complete a precision grip. During each precision grip 5 pulses at 5Hz will be applied. In total, 8 blocks of 10 trains of 15 pulses at 5Hz separated by inter train interval of 10s will be applied (1200 pulses). Each block will be separated by 30s of rest. The periods of stimulation will last approximately 24 minutes.

Measurements before and after rTMS protocol- We will examine: (a) MEPs, SICI, and F-waves (see procedures in AIM1), and (b) EMG and force output. Before rTMS, to examine EMG and force output individuals will receive visual feedback on a computer screen corresponding to 10% of MVC during a precision grip. The target will be presented for 1 second and then it will disappear at intervals of 5-6 seconds. Subjects will be instructed to reach the target as accurately as possible without making any corrections. Three sets of 20 repetitions will be tested. Signals will be acquired and the mean of force displacement plus 1 standard deviation (SD) will be calculated. After rTMS, subjects will not be told whether the visual feedback is derived from their actual or from their previous performance. Then, the visual feedback presented in the computer screen will correspond to mean forces +1SD values exerted prior rTMS.

The Jebsen Taylor Hand Function Test

The JHFT was developed to provide a standardized and objective evaluation of several major aspects of hand function using simulated activities of daily living.

(Jebsen et al. 1969)

The Jebsen Taylor Hand Function Test is a standardized test with high intra-tester ($r = 0.85$; $p > 0.05$) and inter-tester reliability (intraclass correlation coefficient ranging from 0.82 to 1.00). It is designed for adults with neurological or musculo-skeletal conditions involving hand disabilities. The test items include a range of fine motor, weighted and non-weighted hand function activities: (i) writing (copying) a

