Subjects will be instructed to follow a target line on a computer screen as accurately as possible while performing precision grips with simultaneously maximal wrist flexion and extension. Stimulation will be triggered if both movements are performed. See Experiment 1 for rTMS parameters. At each time three targets will be presented separated by approximately 2 seconds of reset on the screen for a total duration of 10 seconds. The period of stimulation will last approximately 24 minutes. Subjects will be randomly assigned to two groups: training + rTMS, and training + sham rTMS. A train of rTMS will be applied during each of the target presentations. The coil will be positioned over the optimal scalp position for activating finger and wrist muscles. Here, 5 pulses at 5 hz will be applied each time that a target appears on the computer screen. In a control task individuals will be asked to perform to follow the same cursor using their lower limb muscles. A total of 1200 rTMS pulses will be applied at 80% of AMT intensity (see more details about rTMS application in AIM 2a).

Training+sham rTMS group- Training will be conducted as described above. For sham rTMS, TMS coil will be positioned in the same location as described above. A second coil will be placed behind the subjects head, and it will discharge in the air using the same stimulation parameters that will be used in the TMS application. During sham stimulation only the coil located behind the subjects head will be triggered. Participants may feel small pressure from the coil positioned on top of their head and hear the click sound during triggering.

Measurements before and after rTMS protocols:

Physiology- We will examine: (a) MEPs, SICI, IHI, and F-wave (See procedures in Aim 1). Precision grip motor performance: We will quantify the following outcomes: (a) Force onset [the time point at which force increases 2SD above force baseline], (b) Force rate (maximum derivative of force (force/s) between force onset and target force), (c) Force area (area between force onset and force decay to zero), and (d) Total force duration (time between force onset and force decay to zero).

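### The primary outcome is a whole class of evoked responses in several muscles, and nothing in the analysis plan limits false-positive error across those measures and muscles

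*Combined protocol and SAP*

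**What the plan says.** The only statement of a primary outcome is in Section C, Methodology: "The primary outcome measures of this study are muscle responses to stimulation with magnetic pulses using TMS and electrical stimulation of a peripheral nerve". The stimulated nerve may belong to either an upper or a lower limb. The same paragraph gives an open-ended muscle list: "such as in the first dorsal interosseous (FDI), biceps brachii (BIC), anterior deltoid (AD), tibialis anterior (TA), hamstring (HAMS) and quadriceps (QUAD".

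Phase 1 (Aim 1) narrows the muscles to three, examining TMS measurements and "motoneuronal excitability in the first dorsal interosseous, and flexor and extensor carpis radialis muscles". Part A lists motor evoked potentials (MEPs), short-interval intracortical inhibition (SICI) and interhemispheric inhibition (IHI) as TMS measures. Part B adds F-wave persistence and F-wave amplitude from peripheral nerve stimulation.

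The later aims refer back to these procedures. Aim 2a: "We will examine: (a) MEPs, SICI, and F-waves (see procedures in AIM1), and (b) EMG and force output". IHI is absent there. Aim 2b: "We will examine: (a) MEPs, SICI, IHI, and F-wave (See procedures in Aim 1".

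For Aim 1, Section G says "Repeated-measures ANOVA and Tukey post hoc test will be used to assess the effect of TASK" and GROUP on physiological measurements. Aims 2a and 2b get the same type of analysis with their own factors. No alpha, ordering of outcomes or adjustment across outcomes is given anywhere.

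**The concern.** Tukey's procedure controls error over pairwise comparisons of factor levels within one ANOVA. It does nothing about running the analysis again for another measure or muscle. The protocol says it will test hypotheses, describes a randomised sham-controlled design and states expected directions. A reader of the results could not tell whether a significant primary finding was singled out in advance or was the most favourable of a dozen or more candidates.

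There is also a mismatch of definition. The Aim 2a hypothesis (Sections A and C) rests on voluntary output measured by EMG and the Jebsen Taylor Test, and the Aim 2b hypothesis rests on precision grip training outcomes. Neither belongs to the evoked-response class that Section C calls primary, so the hypotheses cannot be used to infer which primary test counts in those aims.

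**Working it through.** The plan gives no alpha, power or family-wise error rate, so it has no figure of its own to reproduce here.

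**Inputs from the documents**
- Aim 1: MEP, SICI, IHI, F-wave persistence, F-wave amplitude = 5 measures; 3 muscles; 5 × 3 = 15.
- Aim 2a: as Aim 1 without IHI = 4 measures; 4 × 3 = 12.
- Aim 2b: the five Aim 1 measures; 5 × 3 = 15.
- Aim 1 hypothesis only (intracortical inhibition, F-wave persistence, F-wave amplitude): 3 × 3 = 9.

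Carrying three muscles into Aims 2a and 2b follows their references back to Aim 1.

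**Assumptions, because the documents are silent**
- Two-sided alpha of 0.05 per test.
- One test per measure and muscle. Section G does not say whether muscle is a factor, so the alternative is shown too.
- Every null hypothesis true.
- Common correlation ρ between test statistics, from 0 to 0.8.

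**Formulas**
- Independent tests: 1 − 0.95^m.
- Correlated tests: 1 − ∫ φ(u) [Φ((c − √ρ·u)/√(1−ρ)) − Φ((−c − √ρ·u)/√(1−ρ))]^m du, with c = 1.96. This is for exchangeable normal statistics, that is, single-degree-of-freedom contrasts.

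**Results: chance of at least one false positive**

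| Family | m | Independent | ρ = 0.5 | ρ = 0.8 |
|---|---|---|---|---|
| Aim 1, or Aim 2b | 15 | 1 − 0.95^15 = 54% | 36% | 20% |
| Aim 2a | 12 | 1 − 0.95^12 = 46% | 32% | 19% |
| Measures in the Aim 1 hypothesis | 9 | 1 − 0.95^9 = 37% | 27% | 17% |
| Muscle as a factor, one test per measure (Aims 1, 2b) | 5 | 1 − 0.95^5 = 23% | 18% | 13% |

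**Sensitivity to alpha.** At 0.01 per test, 15 independent tests give 1 − 0.99^15 = 14%.

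**What the count leaves out.** Cervicomedullary responses, motor thresholds, bilateral recordings, the other muscles in the general list, and the extra F tests in each two-way ANOVA are not counted.

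**The case against.** The best defence is that the hypotheses are narrower than the outcome list. The Aim 1 hypothesis names intracortical inhibition and the two F-wave measures, gives a direction (reduced), and joins cortical and spinal inputs. MEPs and IHI are not in it. Counting only errors in the predicted direction, nine tests give 1 − 0.975^9 = 20% if independent and 13% at correlation 0.5. A joint cortical-and-spinal claim would not rest on one false positive. This stands as a reason not to say that any single significant test would support the Aim 1 hypothesis. It does not remove the problem: Section C still calls the whole class primary, nine tests remain over three muscles, and the Aim 2a and 2b hypotheses give no such help.

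A second defence is that evoked responses in hand and wrist muscles of the same person are correlated, and that muscle could be a factor in the model. Both would lower the risk, but every row of the table stays above 5%.

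A reader might go further and infer that a false positive is more likely than not in each aim. The documents do not support that. Among the per-aim figures above, only 15 fully independent tests exceed 50%, and independence is implausible here. Nor should the Aim 2b force, function and independence outcomes be added to the primary count: Section C confines the primary class to evoked responses.

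**Conclusion.** The concern holds. The primary outcome is an unranked class, and the plan contains no control across its measures and muscles. With 5% tests, one per measure and muscle, and all nulls true, the risk of at least one false positive per aim runs from 19–20% (correlation 0.8) to 46–54% (independence). The narrower readings give 13% to 37%. This is several times the nominal level. For one aim with correlated outcomes it is not more likely than not.

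The absence of control and the mismatch between the primary definition and the Aim 2 hypotheses can be read directly from the text. The percentages depend on the assumed alpha, the correlation and the way the ANOVAs are set up, none of which the documents state. The figures are per aim because the documents do not say whether error is to be controlled per aim or study-wide.

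**What to change.** - State alpha and sidedness.
- For each aim, prespecify a small primary family with one muscle, one time point and one contrast per measure.
- Aim 1: use the three measures its hypothesis names (SICI, F-wave persistence, F-wave amplitude) in the first dorsal interosseous. Test the GROUP contrast during the task, saying whether it is averaged over the flexion and extension conditions or taken in one of them. Apply Holm across the three.
- Aims 2a and 2b: first reconcile the Section C primary definition with the hypotheses (EMG and Jebsen Taylor Test; precision grip training outcomes). Then name one primary measure for each, with the stimulation-by-time contrast (group-by-time in Section G's terms for Aim 2b).
- Say that error is controlled per aim, or split alpha over the three aims. Three unadjusted primary tests give up to 1 − 0.95^3 = 14%; at 0.05/3 = 0.0167 each, 1 − 0.9833^3 = 4.9%.
- Report all other measures and muscles as secondary or exploratory, with Holm or false-discovery-rate adjustment.

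The cost is less power for each adjusted or demoted outcome. At 80% power, the strictest Holm step over three tests multiplies the required sample size by ((2.394 + 0.842)/(1.960 + 0.842))² ≈ 1.33, against about 1.82 for Bonferroni over 15. No new visits or measurements are needed, but reconciling the primary definition changes the protocol text as well as the analysis section.
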